1.2.1.2.1 Results of study LCI699C2201

Results of LCI699C2201 study in CD.

The purpose of the LCI699C2201 study was to determine whether the ability of osilodrostat to inhibit 11 β -hydroxylase could safely reduce UFC (Urinary Free Cortisol) in patients with CD.

This was initially studied over a 10-week treatment duration Proof-of Concept (Part I). Part II of the study aimed to further evaluate the observations from the Part I by enrolling a cohort of patients who participated in Part I and a new cohort (Expansion cohort) of patients and evaluating the long-term efficacy and safety of osilodrostat treatment.

In Part I, osilodrostat was effective in controlling cortisol production in all 12 patients studied. At daily osilodrostat doses between 2 mg twice a day (b.i.d.) and 50 mg b.i.d., 24-hour cortisol decreased rapidly and normalized at least once in all patients studied. In general at 5 mg b.i.d.

patients showed cortisol reduction after 2 weeks (at first cortisol measurement after dose titration).

The primary endpoint, defined as cortisol \leq Upper Limit Normal (ULN) or $\geq 50\%$ decrease from baseline at Day 70, was achieved by all patients. Overall, the mean time to response (UFC normalization or $\geq 50\%$ reduction from baseline) was 34.3 ± 14.1 days. The mean daily dose [\pm Standard Deviation (SD)] of osilodrostat required to reach the primary endpoint was 13.5 ± 13.9 mg b.i.d. with 75% of patients normalizing cortisol on ≤ 10 mg b.i.d. At Day 84, two weeks after osilodrostat was withdrawn, cortisol levels increased to a mean of 4-fold above upper limit of normal (ULN).

Significant decreases in mean plasma cortisol and aldosterone from baseline (-60% and -70%, respectively) and marked increases in their precursors from baseline (11-deoxycortisol [13-fold] and 11-deoxycorticosterone [42-fold], respectively) and ACTH [2.4-fold] were observed at Day 70. These biochemical changes were as expected based on the mechanism of action of the drug, i.e., primarily related to hypocortisolism, hypoaldosteronism, accumulation of their precursors, and increase in ACTH from baseline.

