4.5 Risks and benefits

There is still an unmet need in the treatment of CD: despite available therapies, a substantial number of subjects do not achieve normalization of cortisol, lose biochemical control over time or present medication-related adverse reactions and may stop treatment because of this.

In order to mitigate the potential risks related to the administration of osilodrostat, some procedures will be taking place:

- The starting dose should be the same as the dose provided in the parent osilodrostat study at the time of transition to the roll-over study. However, the investigator can change the dose based on the subject's response; the maximal dose should not exceed 30 mg b.i.d.
- Subjects will be evaluated by the treating investigator for clinical benefit and safety based on the following assessments:
 - Physical examination (every 12 weeks)
 - Body weight / blood pressure (every 12 weeks), 12-lead safety ECG (every 24 weeks), blood chemistry and hematology (every 24 weeks), 11-deoxycortisol and 11 deoxycorticosterone (every 24 weeks), testosterone (every 24 weeks), Urinary Free Cortisol (UFC) (every 12 weeks), serum cortisol as clinically indicated, plasma ACTH (every 12 weeks) and pituitary MRI (every 48 weeks or more frequently if clinically needed).
- AEs and SAEs will be reported continuously and evaluated by the investigator at each visit.
- Drug administration record for dosing of osilodrostat will be completed at baseline and during treatment visits.
- For females, urinary pregnancy test will be performed at each visit (every 12 weeks) and monthly, at home.
- Upon administration of the last drug dose, discontinuation from the study or study end, the patient will have a follow-up visit 30 days later.
- The protocol provides specific guidance for dose modifications and/or stopping rules, due to osilodrostat-related toxicities. In addition, a safety follow-up for liver toxicity and management of QT prolongation have also been included.

Potential subject benefits

There is an unmet medical need in subjects with CS since this is a rare and serious disease but with limited medical treatment options.

An open label, proof-of-concept, single-arm study (CLCI699C2201, LINC 2) has been conducted to assess the safety and tolerability of osilodrostat in patients with CD after 10 weeks of treatment.

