Information about common side effects already known about the investigational drug can be found in the Investigator's Brochure (IB). This information will be included in the subject informed consent and should be discussed with the subject during the study as needed. Any new information regarding the safety profile of the investigational drug that is identified between IB updates will be communicated as appropriate, for example, via an investigator notification or an aggregate safety finding. New information might require an update to the informed consent and then must be discussed with the subject.

Women of child bearing potential must be informed that taking the study treatment may involve unknown risks to the fetus if pregnancy were to occur during the study and agree that in order to participate in the study they must adhere to the contraception requirements.

A copy of the approved version of all consent forms must be provided to the sponsor after IRB/IEC approval.

8 Visit schedule and assessments

Assessment schedule lists all of the assessments when they are performed. All data obtained from these assessments must be supported in the subject's source documentation.

Subjects should be seen for all visits/assessments as outlined in the assessment schedule or as close to the designated day/time as possible. Missed or rescheduled visits should not lead to automatic discontinuation. Subjects who prematurely discontinue the study for any reason should be scheduled for a visit as soon as possible, at which time all of the assessments listed for the final visit will be performed. At this final visit, all dispensed investigational product should be reconciled, and the adverse event recorded on the CRF.

Table 8-1 Assessment Schedule

Visit Name	Category	Protocol Section	Baseline / Enrollment	Visits during Treatment (Week 12 and every 12 weeks (+/- 2 weeks) thereafter)					End of study treatment (EoT)	30 day safety follow-up post last dose of study drug / End of Study	
			W1D1	W12D1	W24D1	W36D1	W48D1	W60D1 Onwards			
Visit Number			1	110	120	130	140	150	1999	FU	
Obtain informed consent	D	7	x								
Study History	D	8.2	x								
Demography	D	8.2	x								
Medical History	D	8.2	x								
Inclusion/exclusion criteria	D	5.1	x								
Blood chemistry	D	8.4.3	x		x		x		x	x	
Hematology	D	8.4.3	x		x		x		x	x	
Physical examination	S	8.4.1	x	x	x	x	x	x	x	x	
Body weight / blood pressure	D	8.4.2	x	x	x	x	x	x	x	x	
UFC (two 24-h specimens)	D	8.4.3	x	x	x	x	x	x	x	x	

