9.2 Study completion and post-study treatment

Study completion is defined as when the last subject finishes their Study Completion visit, and any repeat assessments associated with this visit have been documented and followed-up appropriately by the Investigator, or in the event of an early study termination decision, the date of that decision.

All treated subjects should have a safety follow-up call conducted 30 days after last administration of study treatment. The information collected is kept as source documentation. All SAEs reported during this time period must be reported as described in [Section 10.1.3](#). Documentation of attempts to contact the subject should be recorded in the source documentation.

10 Safety monitoring and reporting

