12.5.1 Safety endpoints

12.5.1.1 Analysis set and grouping for the analyses

For all safety analyses, the safety set will be used.

The overall observation period will be divided into two mutually exclusive segments:

1. on-treatment period: from day of first dose of study medication in this study to 30 days after last dose of study medication
2. post-treatment period: starting at day 31 after last dose of study medication.

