#### 7.4.2 Laboratory parameters

Laboratory data summaries will include all assessments available for the lab parameters collected no later than 30 days of safety follow-up whichever is later after the last study treatment administration date using data from all sources. All laboratory assessments will be listed and those collected later than 30 days after the last study treatment date will be flagged in the listings.

Grading of laboratory values will be assigned programmatically as per NCI Common Terminology Criteria for Adverse Events (CTCAE) version 4.03 or higher. The calculation of CTCAE grades will be based on the observed laboratory values only, clinical assessments will not be taken into account. CTCAE version 5.0 will be applied and an extract of the tests that can be graded is reported in attachment 8.3.

CTCAE Grade 0 will be assigned for all non-missing values not graded as 1 or higher. Grade 5 will not be used. For laboratory tests that are graded for both low and high values, summaries will be done separately and labeled by direction, e.g., sodium will be summarized as hyponatremia and hypernatremia.

---

Study Code: CLCI699C2X01B

For laboratory tests where grades are not defined by CTCAE, results will be categorized as low/normal/high based on laboratory normal ranges.

For laboratory tests where grades are defined by CTCAE:

- Summary table for AEs of grades 3 or 4
- Shift tables using CTCAE grades to compare baseline to the worst on-treatment value
- Worst post-baseline CTCAE grade (regardless of the baseline status). Each patient will be counted only once for the worst grade observed post-baseline

For laboratory tests where grades are not defined by CTCAE,

- Shift tables using the low/normal/high/ (low and high) classification to compare baseline to the worst on-treatment value

The following listings will be produced for the laboratory data (hematology, and biochemistry):

- Listing of all laboratory data with values flagged to show the corresponding CTC grades the classifications relative to the laboratory reference ranges
- Listing of notable laboratory abnormalities (i.e., CTC grade 3 or 4 laboratory toxicities).

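### Off-drug values from the 30-day follow-up can enter the worst on-treatment shift tables for labs, vital signs and ECG; UFC is the clearest case

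*Protocol*

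**What the plan says.** **Window.** Protocol 12.5.1.1, which governs all the safety analyses, defines on-treatment as "from day of first dose of study medication in this study to 30 days after last dose of study medication" and post-treatment as "starting at day 31 after last dose of study medication". SAP 7.4.2 uses the 30-day limit for laboratory summaries and flags later values in the listings. Its wording refers to the later of two limits but names only one. SAP 7.4.3 (vital signs) and 7.4.4 (ECG) state no window, so the protocol definition applies to them.

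**Follow-up measurements.** The last column of Table 8-1 is headed "30 day safety follow-up post last dose of study drug / End of Study". The tolerance of 2 weeks either way belongs to the visits during treatment; none is given for follow-up. Blood chemistry, hematology, UFC, plasma ACTH, steroid precursors, testosterone, the "Body weight / blood pressure" row and the ECG are marked in this column. Pituitary MRI is not.

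**Summary measure.** For graded tests, SAP 7.4.2 plans "Shift tables using CTCAE grades to compare baseline to the worst on-treatment value". Ungraded tests get the same comparison in low/normal/high categories, and SAP 7.4.3 and 7.4.4 plan a shift to the worst on-treatment result. Under SAP 4.1.1, baseline is the parent study's end-of-treatment visit.

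**Withdrawal data.** Protocol 1.2.1.2.1 reports for Part I of study C2201 that, "two weeks after osilodrostat was withdrawn, cortisol levels increased to a mean of 4-fold above upper limit of normal".

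**Visit or call.** Protocol 4.5 says that after the last dose "the patient will have a follow-up visit 30 days later". Protocol 9.2 says: "All treated subjects should have a safety follow-up call conducted 30 days after last administration of study treatment".

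**The concern.** A 30-day tail is a familiar rule for adverse events, where a late-onset event may still be due to the drug. A measured value is different: it describes the patient's state on the day of sampling. If the patient stopped osilodrostat a month earlier, a high UFC on that day is more naturally read as loss of control after withdrawal than as a result on treatment.

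The comparison is also lopsided. Inclusion criteria 1 and 2 require patients to be receiving osilodrostat and benefiting from it, so baseline is an on-drug value. The other side of the shift is a maximum that can include an off-drug value. A patient controlled at every treatment visit who rebounds after stopping would be tabulated as high on treatment.

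The follow-up visit is also targeted at the last day of the window, so a one-day scheduling difference decides whether its values enter the laboratory summaries and the worst on-treatment shifts. These tables serve the secondary safety objective in Protocol 12.5.

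**Working it through.** The plan states no figure to reproduce: Protocol 12.8 gives no sample size and 12.4.2 no hypothesis. The check is on timing, classification and direction.

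**1. Timing of the rebound.** Part I lasted 10 weeks (Day 70) and the off-drug measurement was at Day 84.
- Days off drug: 84 − 70 = 14, which agrees with the stated two weeks.
- Window remaining: 30 − 14 = 16 days, and 16/30 = 53%.

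The documented rebound therefore falls well inside the period labelled on-treatment.

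**2. Classification at the boundary.** Under Protocol 12.5.1.1:

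| Follow-up day after last dose | Period |
|---|---|
| 28 | on-treatment |
| 30 | on-treatment |
| 31 | post-treatment |
| 35 | post-treatment |

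**3. Where UFC falls.** Protocol 8.4.3 lists UFC among the laboratory evaluations. SAP attachment 8.3 gives it no CTCAE grade. By SAP 7.4.2 it belongs in the low/normal/high shift to the worst on-treatment value. This is an inference: SAP 7.4.2 does not name UFC, and its planned listings mention only hematology and biochemistry.

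**4. Direction and possible size (illustration only).** Let k be the number of on-drug visits, p the chance of an abnormal value per on-drug visit, and q the chance at an off-drug follow-up counted as on-treatment. Visits are assumed independent.
- Without follow-up: 1 − (1 − p)^k
- With follow-up: 1 − (1 − p)^k × (1 − q)
- Increase: q × (1 − p)^k, which is never negative and never exceeds q

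Example with k = 6, p = 1%, q = 10%: 1 − 0.99^6 = 5.9%; 1 − 0.99^6 × 0.90 = 15.3%; increase 9.4 points.

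For k from 3 to 11 and p from 1% to 3%, the incidence without follow-up is 3.0% to 28.5%. The increase is:

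| Assumed q | Increase (percentage points) |
|---|---|
| 1% | 0.7 to 1.0 |
| 10% | 7.2 to 9.7 |
| 30% | 21.5 to 29.1 |
| 50% | 35.8 to 48.5 |

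The values of k, p and q are assumptions. For a measure often out of range on drug, the increase is smaller. Protocol 1.2.1.2.1 gives 15 of 19 patients with normal cortisol at Week 22 of Part II, leaving 4/19 = 21% not recorded as normal, including any who did not complete. With p = 4/19 and k = 6, (15/19)^6 = 0.24, so q = 50% would add about 12 points.

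**The case against.** **It is a convention, and a cautious one.** The 30-day window is explicit, the study is single-arm and descriptive, and an extra visit can only raise a worst-value count. This stands, and it limits the severity. It does not make an off-drug value an on-treatment one.

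**The values stay visible.** SAP 7.4.2 lists all laboratory data and separates high from low, so a rebound in one direction does not hide an on-drug abnormality in the other. SAP 7.4.3 lists vital signs by visit and summarises change over time. This stands as mitigation, but the summary tables themselves do not separate the two states.

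**Not everyone is off drug.** A reader might infer that every follow-up sample is taken a month after stopping. The documents do not support that. Protocol 9.1.1 withdraws patients when osilodrostat becomes commercially available in their country, and some may be taking commercial drug at day 30. Their share is not given.

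**The samples may not exist.** Protocol 9.2 describes a call, which yields no laboratory, blood pressure or ECG data. Protocol 4.5 and Table 8-1 describe a visit. The passages conflict.

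**The evidence is narrow.** The rebound figure is for cortisol only, in 12 patients treated for 10 weeks at doses up to 50 mg b.i.d., above this study's 30 mg b.i.d. ceiling. A reader might infer that blood pressure, potassium, HbA1c and QTcF are shown to be distorted. The documents give no off-drug data for them.

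**The boundary does not govern everything.** Most ECG notable-abnormality criteria in SAP 7.4.4 count post-baseline values with no upper time limit. Day 30 against day 31 makes no difference there; the boundary matters only for the ECG shift table.

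**Simply shortening the window would lose data.** Table 6-3 requires weekly liver tests after stopping for liver toxicity, and a peak in those weeks belongs in a safety table. The final visit after premature discontinuation is to be held as soon as possible (Protocol section 8), so it may itself be off drug. Both points stand, so ending the window at the end-of-treatment visit would be the wrong remedy.

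**Conclusion.** The point holds in a limited form. Protocol 12.5.1.1, Table 8-1 and SAP 7.4.2 to 7.4.4 together allow off-drug measurements to be tabulated as worst on-treatment values against an on-drug baseline. The documents support this most directly for UFC. For blood pressure, potassium, HbA1c and QTcF it is plausible but unquantified.

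No overall size can be given. A reader might want the share of follow-up visits that count as on-treatment, but with no visit window in the documents this depends wholly on the assumed spread of days: an even spread over days 23 to 30 gives 8/8 = 100%, and over days 30 to 37 gives 1/8 = 12.5%.

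The conclusion assumes that follow-up measurements are actually collected, and it applies only to patients who have stopped osilodrostat. Severity is minor: nothing is tested, and the primary AE/SAE endpoint is unaffected. It is a cheap improvement.

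**What to change.** - Keep the 30-day window for AEs and deaths.
- Keep the 30-day worst-value tables for labs, vital signs and ECG, so that peaks after stopping, such as liver tests, are not lost.
- Add a worst-value shift for the same measures, limited to measurements up to last dose plus a short lag that the SAP fixes and justifies in advance.
- Summarise later off-drug values, including the 30-day follow-up visit, in their own column whatever the exact visit day. Flag whether the patient continued on commercial drug.
- State in SAP 7.4.3 and 7.4.4 which window applies, and clarify the limit in SAP 7.4.2.
- Reconcile Protocol 9.2 (call) with Protocol 4.5 and Table 8-1 (visit with assessments).

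The analysis changes need SAP wording, an analysis flag and one extra set of tables. The flag for commercial continuation needs that status to be available from the disposition data. None of the interim tables in SAP 2.3 is a laboratory, vital-sign or ECG shift table, so the change can be made before the final analysis without altering a table on that list.

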12.5.1.2 Adverse events (AEs)

Summary tables for adverse events (AEs) will include only AEs that started or worsened during the on-treatment period, the ***treatment-emergent*** AEs.

The incidence of treatment-emergent adverse events (new or worsening from baseline) will be summarized by system organ class and or preferred term, severity (based on CTCAE grades), type of adverse event, relation to study treatment.

Serious adverse events, non-serious adverse events during the on-treatment period will be tabulated.

All deaths (on-treatment and post-treatment) will be summarized.

All AEs, deaths and serious adverse events (including those from post-treatment periods) will be listed and those collected during post-treatment period will be flagged.

12.5.1.3 Laboratory abnormalities

Grading of laboratory values will be assigned programmatically as per NCI Common Terminology Criteria for Adverse Events (CTCAE) version 4.03. The calculation of CTCAE grades will be based on the observed laboratory values only, clinical assessments will not be taken into account.

CTCAE Grade 0 will be assigned for all non-missing values not graded as 1 or higher. Grade 5 will not be used.

For laboratory evaluations where grades are not defined by CTCAE v4.03, results will be categorized as low/normal/high based on laboratory normal ranges.

Laboratory data will be listed and summarized as appropriate. Details of specific analyses will be given in the Statistical Analysis Plan.

12.5.1.4 Other safety data

Vital signs

Vital signs (BP and body weight) will be listed and summarized as appropriate. Details of specific analyses will be given in the Statistical Analysis Plan.

Pituitary MRI

Tumor volume and longest dimension will be evaluated as defined in Section 8.4.6

The longest dimension (in mm) and tumor volume (if evaluated) will be listed and summarized as appropriate. Details of specific analyses will be given in the Statistical Analysis Plan.

12.6 Analysis of exploratory endpoints

Not applicable.

12.7 Interim analyses

No formal interim analysis is planned for this study. Interim analysis may be performed for regulatory purposes if deemed necessary.

12.8 Sample size calculation

Not applicable.

13 Ethical considerations and administrative procedures

13.1 Regulatory and ethical compliance

This clinical study was designed, shall be implemented and reported in accordance with the ICH Harmonized Tripartite Guidelines for Good Clinical Practice, with applicable local regulations (including European Directive 2001/20/EC and US Code of Federal Regulations Title 21), and with the ethical principles laid down in the Declaration of Helsinki.

13.2 Responsibilities of the investigator and IRB/IEC

Before initiating a trial, the investigator/institution must obtain approval/favorable opinion from the Institutional Review Board/Independent Ethics Committee (IRB/IEC) for the trial protocol, written informed consent form, consent form updates, subject recruitment procedures (e.g., advertisements) and any other written information to be provided to subjects. Prior to study start, the investigator is required to sign a protocol signature page confirming his/her agreement to conduct the study in accordance with these documents and all of the instructions and procedures found in this protocol and to give access to all relevant data and records to IQVIA monitors, auditors, Recordati/ Quality Assurance representatives, designated agents of

Recordati, IRBs/IECs, and regulatory authorities as required. If an inspection of the clinical site is requested by a regulatory authority, the investigator must inform IQVIA (and in turn Recordati) immediately that this request has been made.

13.3 Publication of study protocol and results

The protocol will be registered in a publicly accessible database such as clinicaltrials.gov and as required in EudraCT. In addition, after study completion (**defined as last patient last visit**) and finalization of the study report the results of this trial will be disclosed to Competent Authorities, Ethics Committees and Investigators, submitted for publication and posted in a publicly accessible database of clinical trial results, such as Health Authority websites (e.g. Clinicaltrials.gov, EudraCT etc.).

In accordance with Recordati publication policy, multicenter studies should be submitted for publication in peer-reviewed journals before, or in parallel with, any secondary publication (e.g. subgroups analyses or results from individual centers). A coordinating investigator will be designated by mutual agreement. Authorship will be determined by mutual agreement and in line with International Committee of Medical Journal Editors authorship requirements.

In order to protect proprietary information and to provide comments, Recordati reserves the right to review all manuscripts and abstracts before their submission for publication or presentation at scientific meetings.

